## 7.3. PACKAGING AND LABELLING

Study drug will be provided by the sponsor (or delegate) as 3-monthly kits. Each 3-monthly kit will contain 13 Aluminum (Al) pouches containing two PVC/Al blisters of two different colors (colored Al foil), i.e. sufficient to cover treatment for 13 weeks for each subject. All the 13 pouches and their corresponding blisters will be labelled with the same kit number, to be provided to a given subject.

**Part A – 3-monthly treatment: 13 pouches/3-monthly kit – 26 blisters (13 blisters of each color) – 7 tablets/blister.**

Population	55	55	55	55	55	55
Arm	Placebo	50mg	75mg	100mg	200mg	75mg
Blister with color A						
Blister with color B						

**Part B – 3-monthly treatment: 13 pouches/3-monthly kit – 26 blisters (13 blisters of each color) – 7 tablets/blister.**

Population	55	55	55	55	55	55
Arm	Placebo/100mg	50mg	75mg	100mg	200mg	50 or 75 or 100mg
Blister with color A						
Blister with color B						

On Day 1 and at Week 12 visit, the subject will be given one 3-monthly kit for a total of 13 weeks (i.e. including one extra week to cover the allowed time window for visit scheduling).

Each day, from Day 1 to the last day of Week 24 inclusive, the subject will have to swallow two tablets, one from each blister of different color and included in a same pouch.

In each 3-monthly kit, all 13 pouches will have a label including a tear-off part. The non-tear off part will remain affixed to the pouch and one of the 13 tear-off part containing the study number and the kit number will be placed into a drug accountability booklet at site.

Labels will be printed in the local language of the countries where the study will take place in accordance with applicable local regulations, the recommendations of GMP guideline (Annex 13) and FDA 21 CFR 312.6 part.

The label on the secondary packaging will indicate at least the following items:

- Protocol number
- Kit number
- Batch number
- Storage conditions
- Sponsor name and address
- Expiry date (for EU only)

Label examples are filed in the study file at the Investigator's site and in the trial master file.

#### **7.4. PREPARATION, HANDLING AND STORAGE**

The investigational site will store the IMP according to the specifications of the sponsor. The IMP storage conditions will be indicated on each pouch.

The storage facility at site should be locked and temperature-controlled.

The storage temperature at the clinical site must be recorded by using a minimum/maximum thermometer or electronically 24 hours a day with printouts available on request.

The IMP may be dispensed only by the pharmacist or by a member of staff specifically authorized by the Investigator.

Any deviations from the recommended storage conditions at the site should be immediately reported to the sponsor (or delegate), and the IMP should not be used until authorization has been given by the sponsor (or delegate).

#### **7.5. IMP ACCOUNTABILITY**

The Investigator is responsible for ensuring IMP accountability, including reconciliation and maintenance of drug records.

- Upon receipt of the IMP, the Investigator (or pharmacist) will check for accurate delivery and acknowledge receipt. A copy of acknowledgement of receipt will be retained in the investigator file.
- The dispensing of the IMP will be carefully recorded on the appropriate drug accountability booklet provided by the sponsor (or delegate) and an accurate accounting will be available for verification by the study monitor at each monitoring visit.
- IMP accountability records will include:
  - Confirmation of IMP delivery to the trial site

- The inventory at the site of IMP delivered
- The use of each dose by each subject
- The return to the sponsor (or delegate) or alternative disposition of unused IMP
- Dates, quantities, batch numbers and kit numbers assigned to the subject.
- The Investigator should maintain records that adequately document:
  - The subjects were provided with the doses specified by the protocol/amendment(s).
  - All IMP provided were fully reconciled.

Unused IMP must not be discarded or used for any purpose other than the present study. IMP that has been partially dispensed to a subject must not be re-dispensed to a different subject.

The Study monitor will periodically check the IMP accountability booklet and check all IMP dispensations and returns (both unused and used treatments) during the entire study period and prior to making arrangements for their return to the sponsor (or delegate) or authorizing their destruction by the study site in agreement with the sponsor.

#### **7.6. ASSIGNMENT TO TREATMENT GROUPS**

Prior to the start of the study, a randomization list and a treatment kit list will be generated by a designated statistician from the sponsor or delegate to be transmitted to the assigned clinical packaging organization for labelling and to a fully integrated IWRS.

Kit numbers assigned by the IWRS will start from K0001, K0002, K0003 etc. (5-characters) and will correspond to the kit number indicated on the label of the study drug.

Complete blocks of treatment materials will be assigned to the investigational sites. However, the shipment of the treatment kits (as individual 3-monthly kits) to each site will be made on an as-needed basis depending on the site screening rate.

Subjects will be randomized to one of six treatment groups in a 1:1:1:1:1:1 ratio, stratified by site.

#### **7.7. ASSESSMENT OF INVESTIGATIONAL MEDICINAL PRODUCT COMPLIANCE**

Each subject must be instructed to bring with her to each visit both opened and unopened IMP packages, in order to allow the assessment of compliance with study treatment.

The decision to withdraw a non-compliant subject from the study will be discussed between the Investigator and the sponsor. A blind review meeting will take place prior to unblinding. Subjects with poor compliance and other significant protocol violations may be excluded from the Per Protocol Analysis Set.

During the entire study period, the study monitor will perform drug accountability and the assessment of compliance with study treatment by checking both opened and unopened IMP packages, as well as empty blisters.

## 7.8. METHOD OF BLINDING

The study design is double blind. The randomization list will be secured in a computer file with restricted access to only the designated personnel including those responsible for labelling and handling the study medication until the study database is locked and ready to be unblinded.

Every effort will be done to keep the Investigator, the subject and the sponsor study personnel fully blinded. Individual E2, SHBG and LH levels will not be communicated to them.

## 7.9. EMERGENCY UNBLINDING

The study blind may be broken for an individual subject **only in the case of an emergency** when knowledge of the IMP is essential for the clinical management of the subject. The Investigator can break the blind for a subject by using the IWRS that permits immediate unblinding. In case of doubt as to whether emergency unblinding is necessary, the Investigator should contact the sponsor prior to breaking the study blind.

In the case of a code break, the Investigator must inform the sponsor immediately without revealing the code to the sponsor study personnel and the complete Study Team.

If a Serious Adverse Event (SAE) is reported, the ObsEva (or delegate) Representative for Pharmacovigilance may unblind the treatment assignment for the affected subject. When applicable, an expedited report will be sent to all Investigators in accordance with regulations.

## 7.10. TREATMENT OF OVERDOSE AND MISUSE

An overdose is defined as any dose (i.e. quantity of drug given per administration or per day) above the maximum dosage defined in the protocol.

Misuse is the term used if more precise information is not available and additional information is needed to determine if there was a “medication error”, “drug abuse” or “overdose”.

Any details of overdose or misuse must be recorded in the eCRF.

Any case of overdose or misuse associated with an AE or a SAE must be reported as per the instructions detailed in Section 8.2.

The effects of an overdose of OBE2109 are unknown, but single and repeated doses of up to 400 mg were shown to be safe in a Phase 1 single and multiple ascending dose study, and doses up to 200 mg daily for 3 months were safe in endometriosis subjects (see Section 1.5).

## 7.11. OTHER SUPPLIES TO BE USED IN THE STUDY

A limited quantity (as per Investigator’s judgement) of standard doses of ibuprofen and/or acetaminophen/paracetamol will be given to the subject as standard rescue medication for endometriosis pain. Ibuprofen and acetaminophen/paracetamol will be sourced by the investigational site and reimbursed by the sponsor.

The subject will have to record the intake of the analgesic rescue medication, including dose, in her eDiary.

Condoms with spermicide will also be provided by the sponsor free of charge to the subject.

## 8. ADVERSE EVENTS AND SERIOUS ADVERSE EVENTS

Comprehensive assessments of any apparent toxicity experienced by the subject will be performed throughout the course of the study from the time of subject's signature of informed consent. Study site personnel will report any AE, whether observed by the Investigator or reported by the subject (see section 8.2.1, Eliciting Adverse Events).

The safety profile of OBE2109 will be assessed through the recording, reporting and analysis of baseline medical conditions, AEs, physical examination findings, vital signs, laboratory tests, BMD assessments.

The reporting period for AEs is described in section 8.5.

### 8.1. ADVERSE EVENTS

#### 8.1.1. Definitions

##### Adverse Event:

An adverse event (AE) is defined as any untoward medical occurrence in a clinical trial subject administered an investigational medicinal product (IMP) and which does not necessarily have a causal relationship with this treatment. It can therefore be any unfavourable sign (including an abnormal laboratory finding), symptom, or disease temporally associated with the use of an IMP, whether or not considered related to the IMP.

Events occurring prior to first IMP administration in the study are not considered AEs per se, but an event that could be due to the disease or specific circumstances in which the subject has been placed (i.e. withdrawal of a previous drug to enter the study or "protocol-related"). For monitoring purposes, any protocol-related event, as assessed by the Investigator, should be reported on an AE form or an SAE form, as appropriate.

##### Severity:

The severity of AEs must be assessed by the Investigator according to the following definitions. The term "severity" is used to describe the intensity of a specific event. This has to be distinguished from the term "serious".

Mild:	The subject is aware of the event or symptom, but the event or symptom is easily tolerated (e.g. no reduction in daily activities is required).
Moderate:	The subject experiences sufficient discomfort to interfere with or reduce her usual level of activity.
Severe:	Significant impairment of functioning: the subject is unable to carry out usual activities and/or the subject's life is at risk from the event.

**Causality assessment:**

The causality assessment of an AE to the IMP will be rated as follows by the Investigator:

Not related:	There is no reasonable possibility of causal relationship between an AE and IMP.
Related:	There is at least a reasonable possibility of a causal relationship between an AE and an IMP. This means that there are facts (evidence) or arguments to suggest a causal relationship.

**Unexpected Adverse Event:**

Any AE which is not consistent in specificity or severity with the current Investigator's Brochure, including all amendments, is considered unexpected.

**Outcome:**

Outcome describes the status of the AE. The Investigator will provide information regarding the subject outcome of each AE, and the options include:

Fatal	Termination of life as a result of an AE.
Not recovered/not resolved	Subject has not recuperated or the AE has not improved.
Recovering/resolving	Subject is recuperating or the AE is improving.
Recovered/resolved	Subject has recuperated or the AE has resolved.
Recovered with sequelae/resolved with sequelae	AE has resolved, but the subject has symptoms or pathology.
Unknown	Unknown, not observed, not recorded, or refused.

**Action taken regarding study drug:**

The Investigator will provide the action taken regarding study drug in response to each AE, and the options include:

Dose not changed	No change in the administration of study drug.
Drug (study drug) interrupted	Temporary interruption (termination) in the administration of study drug.
Drug (study drug) withdrawn	Administration of study drug is terminated (no further dosing).

Unknown

Unknown, not observed, not recorded, or refused.

### **8.1.2. Abnormal laboratory findings and other objective measurements**

Abnormal laboratory findings and other objective measurements (e.g. vital signs) must be reported as an AE only if assessed by the Investigator as “clinically significant” e.g. meeting at least one of the following conditions:

1. The abnormality suggests a disease and/or organ toxicity AND this abnormality was not present at the screening visit or is assessed as having evolved since the screening visit.
2. The abnormality is a Serious Adverse Event.
3. The abnormality results in discontinuation of the IMP.
4. The abnormality requires medical intervention or concomitant therapy.

The Investigator must initial and date each laboratory report/eCRF page and note directly on the report/eCRF page whether or not each out-of-range laboratory result is clinically significant. The outcome of this assessment will be reported using an AE or SAE form, as appropriate.

When reporting an abnormal finding for laboratory parameters or other objective measurements on the AE page of the eCRF, a clinical diagnosis should be recorded rather than the abnormal value itself, if available (for example, “anaemia” rather than “decreased red blood cell count”).

For all of these AEs, whether or not related to the treatment, the laboratory test(s) will be followed-up as appropriate.

### **8.1.3. Baseline Medical Conditions**

Medical conditions present at the initial study visit are defined as Baseline Medical Conditions. These medical conditions should be adequately documented on the “medical history page of the eCRF”. Baseline Medical Conditions that worsen in severity or frequency during the study should be recorded and reported as AEs.

### **8.1.4. Exacerbation of endometriosis**

In this protocol, symptoms and signs of exacerbation or worsening of endometriosis will usually be captured in the context of efficacy assessment. Therefore, symptoms, exacerbation or worsening of endometriosis will NOT be considered as AEs nor captured on the AE page of the eCRF unless clinically significant AND not consistent with the anticipated natural progression of the disease. Lack of efficacy of the study drug is NOT considered as an AE.

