### 5.2.2. Exclusion Criteria

To be eligible for inclusion in this study the subject must **not** meet any of the following criteria:

1. The subject is pregnant or breast feeding or is planning a pregnancy within the duration of the treatment period of the study.
2. The subject is less than 6 months postpartum or 3 months post-abortion/miscarriage at the time of entry into the screening period.
3. The subject had an interventional surgery for endometriosis performed within a period of 60 days before screening.
4. The subject had a hysterectomy or bilateral ovariectomy.
5. The subject had a tubal sterilization which was performed with ESSURE™.
6. The subject has an in situ copper intra-uterine device (IUD) or an IUD with progestogen.

7. The subject had endometrial ablation resulting in amenorrhea.
8. The subject has at least one ovarian endometrioma with a diameter of 7 cm or greater.
9. The subject is likely to require treatment during the study OR received treatment within a specified period prior to screening with any of the medications listed below:
  - a. Gonadotropin releasing hormone (GnRH) antagonists 3 months
  - b. GnRH agonist injections/ 3-month depot injections 3 months/6 months
  - c. Danazol 3 months
  - d. Oral contraceptives and other sex hormones 1 month
  - e. Depot contraceptives 6 months
  - f. Selective Progesterone Receptor Modulators (SPRMs),  
Selective Estrogen Receptor Modulators (SERMs)  
and aromatase inhibitors 3 months
  - g. Long acting analgesics (i.e. requiring less than  
once daily dosing) 1 day
  - h. Systemic glucocorticoid treatments  
for acute diseases (not depot) 1 month
10. The subject has a history of or current systemic glucocorticoid therapy for treatment of chronic diseases (e.g. Systemic Lupus Erythematosus (SLE), rheumatic arthritis).
11. The subject did not respond to prior treatment with GnRH agonists or GnRH antagonists for endometriosis.
12. The subject has alanine aminotransferase (ALT), aspartate aminotransferase (AST), or total bilirubin levels  $\geq 2$  times the upper limit of normal OR gamma-glutamyl transpeptidase (GGT) level  $\geq 3$  times the upper limit of normal at screening.
13. The subject has a known positive HIV or viral Hepatitis serology.
14. The subject has abnormal uterine bleeding of undiagnosed cause.

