### **6.4. SAFETY OBSERVATIONS AND MEASUREMENTS**

#### **6.4.1. Adverse Events**

AE data will be collected continuously during the study as described in Section 8.

AE data will be obtained at scheduled study visits based on physical examination, vital signs and biological laboratory assessments (see flowchart in APPENDIX A). In addition, subjects will report AEs spontaneously and/or through questioning.

Complete appropriate data on all AEs experienced for the duration of the reporting period, as defined in section 8, will be reported on an ongoing basis in the AE pages of the eCRF.

A complete physical examination, i.e. weight, examination of organ systems, including thyroid gland, lungs, heart, abdomen, liver, kidneys and peripheral pulses (by palpation, auscultation or percussion), eyes, ears, nose, throat and skin (by inspection) and neurological reflexes will be performed at Screening, on Day 1 and Weeks 12, 24 and 36 visits. In addition, a manual breast examination (by palpation) will be performed at Screening and Week 36. Results of the examinations will be recorded on source subject data file and in the eCRF. Medical conditions present at screening that do worsen in severity and/or frequency during the study will be reported as AEs in the corresponding eCRF page.

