**6.6.2. Prohibited Medicines**

Medication listed in exclusion criteria (see Section 5.2.2) will be prohibited up to week 36.

To consider a subject who is currently taking any prohibited therapies for potential inclusion in this study, the Investigator must ensure that the subject has sufficient washout time prior to enrolling the subject (see Section 5.2.2).

Substrates of cytochrome P450 2C8 (CYP2C8) (e.g. montelukast, repaglinide) and of organic anion transporter 3 (OAT3) (e.g. benzylpenicillin, sitagliptin, ciprofloxacin, pravastatin, rosuvastatin) are prohibited during the treatment period only.

When a prohibited medication or treatment is necessary for the subject's well-being, the sponsor must be notified and possible alternatives are to be discussed before administration of the prohibited medication or treatment whenever possible.

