**6.6.3. Non-Drug Therapies**

Not applicable.

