### 8.3. SERIOUS ADVERSE EVENTS

#### 8.3.1. Definitions

A Serious Adverse Event (SAE) is defined as any untoward medical occurrence or effect that at any dose:

- **results in death,**  
i.e. the AE causes or contributes to the death.
- **is life-threatening,**  
i.e. the AE places the subject at immediate risk of death; it does not refer to AE which hypothetically might have caused death if it were more severe.
- **requires inpatient hospitalization or prolongation of existing hospitalization,**  
i.e. the AE requires at least an overnight admission or prolongs a hospitalization beyond the expected length of stay. Hospital admissions for surgery planned before study entry, for social reasons, for any elective surgery (i.e. plastic surgery) or for normal disease management (including treatment adjustment) are NOT to be considered as SAE according to this criterion..
- **results in persistent or significant disability / incapacity,**  
i.e. the AE resulted in a substantial disruption of the subject's ability to conduct normal activities.
- **is a congenital anomaly / birth defect,**  
i.e. an adverse outcome in a child or fetus of a subject exposed to the IMP before conception or during pregnancy.
- **is an important medical event, i.e. is medically significant ;**

Medical and scientific judgment should be exercised in deciding whether an AE is serious in other situation. Important medical events that may not be immediately life-threatening or result in death or hospitalization but may jeopardise the subject or may require intervention to prevent one of the other outcomes listed in the definition above should also be considered serious. Examples of such events are intensive treatment in an emergency room, or at home for allergic bronchospasm, blood dyscrasias or convulsions that do not result in hospitalization, or development of drug dependency or drug abuse.

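### The AE sections conflict on worsening endometriosis, and with the hospitalisation exemption an admission or operation for it may be reported as neither an AE nor an SAE

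*Combined protocol and SAP*

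**What the plan says.** Two sections set a general rule. Section 8.1.3 states: "Baseline Medical Conditions that worsen in severity or frequency during the study should be recorded and reported as AEs". Section 6.4.1 states: "Medical conditions present at screening that do worsen in severity and/or frequency during the study will be reported as AEs". Neither excepts endometriosis.

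Section 8.1.4 sets a special rule. It expects worsening of endometriosis usually to show up in the efficacy data, and so does not treat it as an AE "unless clinically significant AND not consistent with the anticipated natural progression of the disease".

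Section 8.3.1 defines hospitalisation as a seriousness criterion and then lists admissions that do not count: surgery planned before entry, social reasons, elective surgery and "normal disease management (including treatment adjustment) are NOT to be considered as SAE according to this criterion".

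On surgery itself, exclusion criterion 3 in section 5.2.2 addresses only the time before entry: "The subject had an interventional surgery for endometriosis performed within a period of 60 days before screening". After entry, section 6.6.2 restricts medicines ("Medication listed in exclusion criteria (see Section 5.2.2) will be prohibited up to week 36"), and section 6.6.3 on non-drug therapies reads "Not applicable".

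**The concern.** Endometriosis is the disease under study and every woman has it at entry, so the general and the special rule apply to the same event and give opposite answers. Within 8.1.4 both conditions must hold before worsening becomes an AE. A flare severe enough for admission or an operation can be clearly significant and still be judged to fit the natural course of the disease, a term the protocol does not define. It is then not an AE under that section, and the exemption in 8.3.1 can remove it from the SAE count as well.

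What is at stake is safety information by dose. Disease-related admissions and operations on placebo or on a dose that does too little are outcomes the sponsor and the Data Monitoring Committee would want to see by arm. Section 10.5.1 gives that committee unblinded safety data, AEs and SAEs. An event classed as neither may not reach it.

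**Working it through.** The plan states no figure on this point, so the check sets the sections side by side.

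**Step 1: does the general rule cover endometriosis?** Section 8.1.3 defines baseline conditions as those present at the initial study visit. Inclusion criterion 3 requires confirmed pelvic endometriosis before screening, and section 6.2.1 records its history at screening. So it does. Section 6.7.2.1 points the same way: its adverse-event reason for discontinuation includes clinically significant worsening of an existing condition, documented on the AE form.

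**Step 2: what does 8.1.4 exclude?** Let S = clinically significant and P = consistent with anticipated natural progression. Section 8.1.4 makes worsening an AE only if S and not-P. It is therefore not an AE whenever P holds, however serious the event.

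**Step 3: apply each section to four cases of worsening endometriosis.**

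| Case | 6.4.1 and 8.1.3 | 8.1.4 | 8.3.1, hospitalisation criterion |
|---|---|---|---|
| Not significant, fits natural course | AE | Not an AE | Does not arise |
| Significant, fits natural course, no admission | AE | Not an AE | Does not arise |
| Significant, fits natural course, unplanned admission or operation with overnight stay | AE | Not an AE | Exempt if seen as normal disease management |
| Significant, does not fit natural course, admission | AE | AE | Exempt only if seen as normal disease management |

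The first three rows show the contradiction. The third row is the gap: a site that follows 8.1.4 and regards the admission as disease management reports neither an AE nor an SAE.

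**Step 4: is the event caught elsewhere?** Section 8.1.4 relies on the efficacy assessment. The endpoints in section 3.1 cover pain scores, bleeding, analgesic use, daily activity, the modified Biberoglu and Behrman scale, the EHP-30 and global ratings. None records an admission or an operation.

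**Step 5: does the protocol use an override elsewhere?** Yes. Section 8.1.2 makes an abnormal laboratory finding reportable if it is an SAE, leads to stopping the IMP, or needs medical intervention or concomitant therapy. Section 8.1.4 has no equivalent.

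**Step 6: size.** The documents give no rate of admission or surgery for endometriosis during the study. With 55 women planned per arm, each missed event is 1/55 = 1.8 percentage points of that arm's incidence. Assuming 0 to 3 such women in an arm, the understatement is 0, 1.8, 3.6 (2/55) or 5.5 (3/55) points. The 0 to 3 is an assumption. Section 5.1.3 plans about 60 sites, or 330/60 = 5.5 women per site on average, so many sites would each choose their own reading.

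**The case against.** The strongest reply is that 8.1.4 is the specific rule and overrides the general ones, so there is no real conflict. Protocols also often keep the disease under study out of the AE listing. The first part is a fair way to read the text, but nothing in 6.4.1 or 8.1.3 says so, and on that reading the gap in the third row remains in full.

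Second, the exemption in 8.3.1 covers the hospitalisation criterion only. Death, life-threatening events, disability and important medical events carry no endometriosis exemption. An SAE is defined as an untoward medical occurrence, and 8.3.2 asks for reports whatever the relationship to treatment. This stands, and it is why the event *may* be missed rather than *will* be. The explanatory text under the hospitalisation and important-medical-event criteria speaks of an AE, however, so 8.1.4 can still block those routes.

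Third, the elective-surgery clause is narrow: "for any elective surgery (i.e. plastic surgery) or for normal disease management (including treatment adjustment) are NOT to be considered as SAE". The example given is plastic surgery, so the clause should not be read as covering an operation for a flare. The gap rests on the disease-management clause.

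Fourth, the event need not vanish. Visits record concomitant treatments, section 6.6 puts concomitant medication in the eCRF, and withdrawals are explained on the exit form. Surgery is not named in any of these, and none is stated to feed the AE or SAE tables.

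**Conclusion.** The point holds as a contradiction between 6.4.1 and 8.1.3 on one side and 8.1.4 on the other, together with a reporting gap that depends on judgment when 8.1.4 is read with 8.3.1. It rests on two readings: that a serious flare can be judged to fit natural progression, and that an unplanned admission for it can be seen as normal disease management. Both are open on the text. Its size cannot be taken from the documents.

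A reader might infer more, and the documents do not support it:

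- **That on-study surgery is not a protocol deviation.** The protocol is silent. Major violations are undefined in 9.4, and 7.7 leaves significant violations to a blind review.
- **That relief from surgery is credited to the drug.** The scoring rule in 9.5.2 uses all non-missing diary days, so scores after surgery do enter the endpoint. An operated woman on placebo would add to the placebo response, however, which works against the drug. Keeping observed scores is also a coherent treatment-policy choice.
- **That the trial loses power.** This needs a surgery rate that the documents do not give and more operations on placebo than on active treatment. If the same share in each arm changed from non-responder to responder, the planned difference would stay at 76.9 - 45.5 = 31.4 points.
- **That expedited regulatory reporting fails.** Section 8.4 limits it to unexpected serious reactions with a reasonable possibility of a causal link, and worsening in line with the natural course would not ordinarily qualify.

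The detailed SAP that section 9.5 says will follow is not in the documents, so its handling of such data cannot be checked.

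**What to change.** 1. Reconcile 6.4.1, 8.1.3, 8.1.4 and 8.3.1 so that one rule for worsening endometriosis applies throughout. If 8.1.4 is meant as an exception, say so in 6.4.1 and 8.1.3.
2. Add a seriousness override to 8.1.4, on the model of 8.1.2: worsening of endometriosis that meets any seriousness criterion in 8.3.1 is reported, whether or not it fits the natural course of the disease.
3. State in 8.3.1 that the normal-disease-management exemption does not cover unplanned admissions for worsening endometriosis.
4. Record surgery for endometriosis during the study in the eCRF, with its date.
5. Optionally, prespecify a sensitivity analysis that counts operated women as non-responders, and leave the primary analysis as it is.

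The cost is a few sentences in four sections and one eCRF item, plus a short entry in the SAP if the optional analysis is adopted. The downside is a few more SAE reports.
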